The primary recruitment site for both aims will be Lumumba Sub-County Hospital (“Lumumba Clinic”), which is located next door to the RCTP. PrEP is included in the Kenyan National HIV Prevention Revolution Road Map [34], in which young women are identified as a priority population, and available at no charge through Lumumba Clinic and other public facilities. A total of 438 young women have received PrEP at this facility, making recruitment highly feasible. Contraception and STI testing/treatment (typically in the setting of symptoms, not routine screening) are also available free of charge. Recruitment may also occur through Kisumu County Hospital, which has a similar clinic and is located a 5 minutes-drive from our study offices.

Aim 1. Develop the *PrEP My Way* intervention

Overview. Using a client-centered approach, we will create a young woman-centered kit consisting of HIV self-testing, PrEP refills, STI self-sampling, and pregnancy tests and contraception (if desired), along with educational materials and kit delivery protocols for peer delivery in the community. We will hold individual interviews and focus group discussions with Kenyan women (age 16-24) in an iterative manner to optimally design *PrEP My Way* (the kit with instructional materials) and peer delivery system (including phone-based communication and kit delivery plans).

The intervention. *PrEP My Way* will be developed through an iterative, client-centered process. However, we anticipate that it will involve one clinic-based visit to safely initiate PrEP and contraception per Kenyan national guidelines [35], followed by quarterly community-based peer delivery of a pre-packaged, visually-appealing kit with pictorial and video guidance (to be

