The above-noted procedures will be repeated at the Month 3 and Month 6 visit. Additionally, at the Month 6 visit, an RA will collect the following data either in the field or at the study site (within the next two weeks):

- Dried blood spot for tenofovir concentration
- Creatinine (point-of-care)
- Socio-behavioral data (quantitative questionnaire; see Table 1)
- Acceptability data (see below)

Acceptability will be determined quantitatively with the Systems Usability Scale (SUS; [49]). This 10-item Likert scale assesses domains including desired frequency of use, complexity, need for support, functionality, irregularities, ease of learning/use, time required for use, confidence, and training needed. Qualitatively, we will explore *PrEP My Way* in accordance with the Unified Theory of Acceptance and Use of Technology (UTAUT; Figure 5) in up to 20 participants purposively selected to

Figure 5. Unified Theory of Acceptance and Use of Technology

reflect high and low usage of the kits. Questions for each model component are described in Table 3.

All quantitative data will be recorded on encrypted tablets in REDCap. Qualitative interviews will be digitally recorded and transcribed. All data will be collected in a private space using the participant's preferred language (KiSwahili, DhoLuo, or English).

Table 3. Questions to be used in assessing PrEP My Way acceptability	
Model component	Question content
Performance expectancy	Perceived usefulness, personal outcome expectations
Effort expectancy	Perceived effort needed to arrange delivery and use the kit components
Social influence	Perceived norms and stigma
Facilitating conditions	Kit delivery, instructional materials, role of the peer
Behavioral intention to use	Attitudes around current and anticipated future use/non-use
Actual use	DBS tenofovir concentration

Participants will then be disenrolled from the study and linked back to the Lumumba Clinic, Kisumu County Hospital, or a similar clinic of their choice, for continuation of PrEP as desired. A small incentive/thank you gift (worth a minimum of ~500 Kenyan Shilling or \$5 US) will be given at that time for transport and completion of study-related activities (not *PrEP My Way* utilization). The estimated time spent with the participant will be ~2 hours at enrollment, 30 minutes at Months 1 and 3, and ~1 hour at Month 6.

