Control condition. After randomization, a study research assistant (RA) will administer the baseline demographic and socio-behavioral questionnaire. Control participants will then continue to receive PrEP and any other desired sexual health services at Lumumba Clinic or Kisumu County Hospital. The study may provide or assist the clinics in obtaining necessary supplies for routine HIV/STI services in the event of supply chain stock outs. The RA will call the control participant in ~3 months to maintain accurate contact information and remind her that the RA will meet her at her 6-month PrEP appointment in the Lumumba Clinic or Kisumu County Hospital for the final study visit. The RA will make a reminder call one week in advance. If the control participant does not wish to continue PrEP or return to the Lumumba Clinic/Kisumu County Hospital, she may come to the RCTP study site for the final study procedures. The RA will then collect the following using the methods described above:

- Dried blood spot for tenofovir concentration
- Socio-behavioral data (quantitative questionnaire)
- Review of Lumumba Clinic/Kisumu County Hospital chart records for HIV and STI testing and pick up of PrEP and contraception; participants may be asked for clarification if chart records are incomplete

Control participants will then be disenrolled and provided with a small incentive/thank you (worth at least~500 Kenyan Shillings or \$5 US) for completion of study-related activities. They will continue to receive PrEP and other sexual health services at Lumumba Clinic, Kisumu County Hospital, or another clinic as desired.

Peer identification and hiring, and oversight. Peers will not be participants. They will be identified from PrEP programs in the Kisumu region. Peers will be 18-30 years old women who have themselves taken PrEP for at least 3 months and are fluent in KiSwahili, DhoLuo, and/or English. If they do not own a smart phone, the study will provide one for showing the *PrEP My Way* video guidance and enabling two-way communication with participants (e.g., SMS, WhatsApp). Although already experienced with PrEP, all peers will be trained about PrEP using Kenyan national guideline materials [35]. They will also undergo sensitivity training, including

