Feasibility. Feasibility will be assessed by the following metrics: 1) receipt of the *PrEP My Way* kit at Months 1, 3, and 6, and 2) ability of the participant to use each aspect of the kit (i.e., the HIV self-test, use of the vaginal swab, and self-administration of medroxyprogesterone [if desired]) per protocol. The intervention will be considered feasible if $\geq 70\%$ (35/50) participants 1) receive a kit and 2) achieve a readable HIV test, usable vaginal swab, and self-injection of medroxyprogesterone, if desired, at $\geq 66\%$ (2/3) of visits.

Acceptability. The *PrEP My Way* intervention will be considered acceptable if $>70\%$ (35/50) participants rate 70% (7/10) items on the SUS as "very good" or higher. The qualitative interview will delve deeply into each of the four domains of the UTAUT model to provide in depth feedback on the intervention.

Primary outcomes- Preliminary impact on PrEP adherence and program retention at 6 months. PrEP adherence will be assessed primarily by DBS for tenofovir diphosphate (TFV-DP) concentration. The TFV-DP concentration will provide an estimate of doses taken over the prior 3 months (see Table 4; [11, 50]). Retention will be assessed by kit receipt in the intervention arm and clinic attendance per clinic records in the control arm at Month 6. Potential influencing and mediating socio-behavioral factors (Table 2) will be explored.

Secondary outcomes. We will assess the following:

Table 4. TFV-DP concentrations in DBS	
Estimated use	Median fmol/punch (IQR)

- Self-reported PrEP adherence at Months 1, 3, and 6 (intervention arm) and Month 6 (control arm). We will use the 3-item scale developed by Wilson et al, which involves different recall tasks (frequency, percent, and rating of adherence) over the prior 30 days [51]
- PrEP persistence over the 6-month period
- Rates of STI testing at Months 1, 3, and 6
- Rates of pregnancy test and contraception pick up at Months 1, 3, and 6
- Cost estimates

Protective*	>1,250
Moderate	900-1,249
Low	<900

*Exact value to be explored (see text)

Analysis

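### The Month 6 DBS may follow the PrEP refill by up to two weeks in the intervention arm but is scheduled at the PrEP appointment in the control arm, so adherence may be measured differently by arm

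*Combined protocol and SAP*

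**What the plan says.** All references are to the combined protocol and SAP.

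- **Kit content.** Under Aim 1, Overview, the intervention is a "kit consisting of HIV self-testing, PrEP refills, STI self-sampling, and pregnancy tests and contraception (if desired". Table 1 lists PrEP as supplied by kit at Months 1, 3 and 6 in the intervention arm.
- **Intervention arm, Month 6** (Aim 2, Intervention condition). After describing kit delivery the text says: "The above-noted procedures will be repeated at the Month 3 and Month 6 visit". It adds that "an RA will collect the following data either in the field or at the study site (within the next two weeks"; the DBS heads the list that follows. Nothing states whether the draw comes before or after the kit is handed over.
- **Control arm, Month 6** (Aim 2, Control condition). The participant is told that "the RA will meet her at her 6-month PrEP appointment in the Lumumba Clinic or Kisumu County Hospital for the final study visit". A woman who does not want to continue PrEP or go back to the clinic has an alternative: "she may come to the RCTP study site for the final study procedures". No date limit is attached. The section then says: "The RA will then collect the following using the methods described above".
- **Outcome** (Outcome measures, Primary outcomes). "The TFV-DP concentration will provide an estimate of doses taken over the prior 3 months". Table 4 puts the protective level above 1,250 fmol/punch and notes that the exact value is still to be explored.
- **Analysis** (Analysis, Primary outcomes). The arms are compared by chi-square on protective versus not. Neither the draw date nor the time since last supply enters the analysis.

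**The concern.** The primary adherence measure looks back from the day of the draw, so the draw has to sit at the same point of the supply cycle in both arms. As written it need not. An intervention participant can receive new PrEP and be sampled up to two weeks later. A control participant on her scheduled path is sampled at the appointment where she would collect hers.

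Any change in pill-taking prompted by the Month 6 supply can then enter the measurement in the intervention arm and not, on schedule, in the control arm. Part of an observed difference in the proportion protected could come from the visit schedule instead of from adherence during the six months under study. That proportion helps decide whether a larger trial is warranted.

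**Working it through.** The plan gives no figure for this point, so there is none to reproduce. The check sets the two schedules side by side, counts days, and then asks how far size and direction can be taken.

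**1. Schedules compared**

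| | Intervention | Control |
|---|---|---|
| Month 6 PrEP source | Kit brought by peer | Clinic |
| DBS timing, scheduled path | At the visit or within two weeks | At the 6-month PrEP appointment |
| Alternative | Field or study site, same two weeks | Study site, no date limit |
| Order of draw and supply | Not stated | Not stated |

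Table 1 shows a DBS by research assistant at Month 6 in both arms and does not settle the timing.

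**2. Share of the look-back**

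Inputs: a maximum delay of 14 days (Intervention condition) and a look-back of three months, about 90 days (Outcome measures).

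- Intervention: 14 / 90 = 15.6%. With 91 or 84 days: 14 / 91 = 15.4%, 14 / 84 = 16.7%.
- Control, sampled at the appointment: 0 / 90 = 0%.

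**3. Direction (illustration only)**

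The documents give no half-life for the marker. I assume first-order accumulation with half-life H between 10 and 25 days. Let k = 2^(−14/H) be the fraction of the visit-day level remaining after 14 days.

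- H = 10: k = 0.379. H = 25: k = 0.678.
- From zero, 14 daily doses reach 1 − k of the daily-dosing plateau: 62% (H = 10) or 32% (H = 25).
- A woman at 4/7 = 57% of plateau who then doses daily reaches 0.571k + (1 − k): 84% (H = 10) or 71% (H = 25).
- A woman already dosing daily stays at plateau.
- A woman who stops at the visit falls to k times her visit-day level: 38% (H = 10) or 68% (H = 25).

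A delayed draw can therefore raise, leave unchanged or lower the result, depending on what she does after the refill. These percentages of plateau cannot be converted into crossings of 1,250 fmol/punch, because the documents give no plateau concentration.

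**4. What a given number of reclassified women would do**

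Inputs: 80 analysed participants (Power), hence 40 per arm at 1:1. Assumed: a true protective rate of 40% in both arms (the control rate in the Power section's example), and a two-sided 5% level, since no level is stated. Each woman reclassified moves the arm difference by 1 / 40 = 2.5 percentage points. If a fraction q of the unprotected intervention women (0.60 × 40 = 24) crossed upward, the apparent rate would be 0.40 + 0.60q:

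| q | Women | Apparent rate | Rejection rate, uncorrected chi-square (exact) |
|---|---|---|---|
| 0 | 0 | 40% | 5.2% |
| 5% | 1.2 | 43% | 6.2% |
| 10% | 2.4 | 46% | 9.0% |
| 20% | 4.8 | 52% | 20.3% |

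This shows how sensitive the comparison would be to a net upward shift. It does not estimate q, for which the documents give no basis.

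**The case against.** The strongest reply is that two weeks is an allowance, and that the plan otherwise points to the same visit. Table 1 places the DBS at Month 6 in both arms, a field draw on the day is permitted, and the contact time of about one hour at Month 6, against 30 minutes at Months 1 and 3, fits research procedures being done at the kit visit. If nearly all draws are same-day, the difference is small. That stands as a limit on size. It does not remove the difference in what is permitted.

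Second, the control section's reference to the methods described above might be read as carrying the two-week allowance over. It more naturally concerns how data are collected. Even on the other reading, the text would need clarifying.

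Third, a reader might infer that post-refill dosing can raise levels in the intervention arm only, that a control woman with the same history could not be reclassified, and that the bias therefore favours the intervention. The documents do not support this:

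- Partly adherent women in either arm may hold unused pills and can take more before a sample without any refill.
- Both arms have advance notice: a peer contact one week before the kit visit, and a research assistant's reminder call one week before the control visit.
- The control fallback is undated, and retention teams follow up missed appointments, so later control draws are foreseeable.
- Kit visits are scheduled with the aim of avoiding gaps in PrEP coverage, which limits the scope for a post-refill rise.
- Delay lowers the level in a woman who stops.

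Finally, this is a pilot of preliminary impact, and the Cost section says effectiveness is not its aim. That bears on how much weight the point deserves, but adherence at six months is still a named primary outcome with a between-arm test.

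**Conclusion.** The concern holds as a difference in measurement between the arms. On the scheduled paths, up to 14 of about 90 look-back days (about 16%) can fall after a fresh supply in the intervention arm and none in the control arm, and the primary analysis takes no account of it. Fourteen days is the maximum, and the count takes the control section at its plain reading.

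Upward reclassification is possible in intervention women who take more PrEP after the refill than before it; downward movement is possible in those who stop. The net direction and size cannot be determined from the documents. The accumulation figures rest on an assumed half-life and the rejection rates on assumed fractions crossing the cut-off; neither is evidence that a bias of that size will occur. This is a modest point, worth acting on because the remedy is cheap and the outcome is primary.

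**What to change.** 1. **One window.** State a single DBS window for both arms, anchored to the same scheduled Month 6 date (for example, 0 to 14 days after it), and apply it to control women sampled at the study site.
2. **Order of draw and supply.** Draw the DBS before Month 6 PrEP is handed over, in either arm, where feasible. A common calendar window does not by itself equalise time since supply, so this step matters most. It concerns the order of sampling only.
3. **Dates.** Record the date of last PrEP supply for every woman. The sample date needs no new field: the section on potential risks and protection already has every sample labelled with study ID and date. Control charts are already reviewed for PrEP pick-up.
4. **Sensitivity analysis.** Repeat the protective-versus-not comparison using only samples drawn on or before the day of Month 6 supply, keeping women who received no Month 6 supply. Because the restriction depends on events after randomisation, it should supplement the intention-to-treat comparison and not replace it.

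The cost is slightly tighter scheduling for the research assistants, who may need to attend the kit visit, and one extra date field.

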Participants will be consented as described in Aim 1, enrolled, and randomized (1:1) using a computer-generated simple randomization sequence to receive *PrEP My Way* or follow up as usual at Lumumba Clinic or Kisumu County Hospital over the next 6 months. The code creating the random allocation order will be generated and maintained by the study analyst (separate from the investigators). A variable size block randomization scheme will be implemented to produce the randomization list. Randomization will be implemented by transcribing onto paper within numbered envelopes. Thus, neither participants nor study staff will be blinded to each participant's randomization arm assignment. Fidelity of randomization will be confirmed with tracking in REDCap.

Study procedures (Some aspects of the planned procedures may change pending input from Aim 1 findings). Study procedures for both arms are summarized in Table 1.

Table 1. Summary of study procedures by arm. Each cell indicates how/where the procedure will take place.								
	M0	M1	M3	M6	M0	M1	M3	M6
	PrEP My Way				Control			
Education (PrEP, sexual health)	Clinic	Peer	Peer	Peer	Clinic	Clinic	Clinic	Clinic
HIV testing	Clinic	Kit	Kit	Kit	Clinic	Clinic	Clinic	Clinic
PrEP	Clinic	Kit	Kit	Kit	Clinic	Clinic	Clinic	Clinic
STI sampling	Clinic [^]	Kit	Kit	Kit	Clinic [^]	Clinic [^]	Clinic [^]	Clinic [^]
Pregnancy testing; contraception	Clinic	Kit	Kit	Kit	Clinic	Clinic	Clinic	Clinic
Questionnaire administration	RA	--	--	RA	RA	--	--	RA
Acceptability scale and interview	--	--	--	RA	--	--	--	--
DBS	--	--	--	RA	--	--	--	RA

Clinic=Lumumba Clinic or Kisumu County Hospital; [^]STI testing done only in the setting of symptoms; RA = research assistant; time and motion studies will also be done at the KEMRI Research Care and Training Program (i.e., the study site), Lumumba Clinic, and Kisumu County Hospital mid-way through the study period

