Intervention condition. A research assistant will administer a baseline demographic and socio-behavioral questionnaire (see Table 2) at enrollment (Month 0) and exchange contact information with the participant. Tentative plans will be made for the first kit delivery at Month 1. The meeting will take place at the location, date, and time preferred by the participant; we anticipate the location will be private (e.g., home or a Safe Space) and should have a bathroom to facilitate hygienic sample collection. The meeting will occur during reasonable working hours to ensure the safety and comfort of peers and participants.

Table 2. Socio-behavioral data to be collected at enrollment and 6 months	
Demographics	Age, residence type (urban/rural, with family/partner), employment/education
Alcohol/substance use	Rapid Alcohol Problems Screen-4* [42], use of marijuana and other drugs
Depression	PHQ-9 ^{*^} [43]
Sexual behavior	Number, type of partners (incl. HIV status), use of condoms, transactional, intimate partner violence [Pulerwitz, PLoS One 2018]
HIV and PrEP stigma	Perceived HIV stigma scale (modified Berger, adapted for Kenya)* [^] [44]; PrEP stigma scale [45] [#]
Belief in PrEP	Knowledge about reduction in HIV risk due to PrEP, Belief in Medicines Questionnaire* [^] [46]
Self-esteem/efficacy	Rosenberg Self-Esteem Scale* [^] [47]

Empowerment	Modified Sexual Relationship Power Scale [48]*^
Clinic satisfaction	Patient-Healthcare Provider Relationship [Stall, JAIDS 2006]^#

* validated, ^utilized previously in Kenya, #this scale will be exploratory as it has not yet been used in the population

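### Minor: the baseline questionnaire follows open-label randomisation in the control arm, and probably in both arms, so baseline self-reports can reflect knowledge of the allocation

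*Combined protocol and SAP*

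**What the plan says.** All references are to the combined protocol and SAP.

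- **Control condition:** "After randomization, a study research assistant (RA) will administer the baseline demographic and socio-behavioral questionnaire".
- **Intervention condition:** "A research assistant will administer a baseline demographic and socio-behavioral questionnaire (see Table 2) at enrollment (Month 0"). No sentence places this before or after allocation. The same paragraph continues "Tentative plans will be made for the first kit delivery at Month 1".
- **Consent, enrollment, and randomization:** the steps are listed as consent, enrolment, then 1:1 randomisation, without the questionnaire. "Randomization will be implemented by transcribing onto paper within numbered envelopes", and "neither participants nor study staff will be blinded" to the arm.
- **Table 2:** "Socio-behavioral data to be collected at enrollment and 6 months". Table 1 likewise shows questionnaires only at Months 0 and 6, in both arms.
- **Analysis, Primary outcomes:** the arms are compared by Chi-square tests on protective drug level and on retention. Logistic models then examine factors influencing adherence and retention: age, self-esteem, empowerment, stigma, depression and alcohol/substance use. The visit that supplies these values is not named. Empowerment and depression are also explored as mediators, with sensitivity analyses of key assumptions.
- **Analysis, Secondary outcomes:** the same variables enter logistic and linear models of any observed differences.
- **Power:** sexual behaviour and reported risk are followed as a secondary analysis. Both come from the same questionnaire.

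**The concern.** A baseline covariate is safe to adjust for because the arm cannot have influenced it. Age keeps that property whenever it is recorded. A self-report of mood, self-esteem, power in a relationship or stigma may not keep it if the woman already knows whether she will receive home delivery with peer support or return to the clinic. The research assistant who asks the questions knows the arm too. If the answers shift, adjusting for them removes or adds part of an apparent arm effect, and a baseline table can show an imbalance that randomisation did not produce.

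The stakes are limited. This is a pilot, and the Cost section says that effectiveness is not its aim. Peer contact begins only at Month 1, so at Month 0 knowledge of the allocation is the only difference between the arms.

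**Working it through.** **1. The order, side by side.**

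| Arm | Stated time of the baseline questionnaire | Before or after allocation |
|---|---|---|
| Control | After randomisation | After, explicitly |
| Intervention | Enrolment (Month 0) | Not stated; the section heading and the kit-delivery planning beside it suggest after |

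Neither arm has a protected pre-allocation value. Figure 4 (participant flow) is not shown in the text available here and might state the order.

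**2. Which analyses use the questionnaire.** The Chi-square tests use arm, drug level and retention only. Feasibility uses kit receipt and kit use; acceptability uses the usability scale and interviews. None of these uses a baseline score. The plan's one relevant figure, about 40% power for 40% versus 60% with 80 participants, is therefore unaffected. It recomputes as 43.1% (pooled normal approximation, two-sided 0.05 assumed) and 36.9% (Fisher), which brackets the rounded figure.

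**3. Possible size in a model that includes arm.** The documents give no shift size, so these inputs are assumptions. Let C be the true baseline score, A the arm (1 = intervention), and d the between-arm shift in SD caused by knowing the arm. The recorded score is X = C + dA. With no intervention effect, logit P(Y) = a + bC = a + bX − bdA. The adjusted arm odds ratio is therefore exp(−bd) = (odds ratio per SD)^(−d).

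| Odds ratio per SD | d (SD) | Adjusted arm odds ratio | Shift in log odds ratio | Shift / SE, 40 per arm |
|---|---|---|---|---|
| any | 0 | 1.00 | 0 | 0 |
| 1.5 | +0.1 / −0.1 | 0.96 / 1.04 | 0.0405 | 0.0405/0.511 = 0.08 |
| 2 | +0.1 / −0.1 | 0.93 / 1.07 | 0.0693 | 0.0693/0.528 = 0.13 |
| 2 | +0.3 / −0.3 | 0.81 / 1.23 | 0.2079 | 0.2079/0.528 = 0.39 |

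The standard errors are medians from simulated trials with six covariates and a 40% outcome at the covariate mean. Forty per arm is the 80 evaluable participants in the Power section. With 150 randomised and 20% lost, 150 × 0.8 / 2 = 60 per arm; the standard errors are then 0.403 and 0.415, and the ratios 0.10, 0.17 and 0.50.

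**4. The covariate's own odds ratio.** In simulation, with arm in the model, a true odds ratio of 2 is recovered as 1.99 to 2.01 for every d from −0.3 to +0.3. Without arm and with no intervention effect it is 1.97 at d = ±0.3. Without arm and with an arm odds ratio of 2.25, it is 1.79 at d = −0.3 and 2.06 at d = +0.3, against 1.94 at d = 0.

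**5. A secondary note on mediator timing.** Empowerment and depression are measured again only at Month 6. The drug level reflects the prior 3 months, and retention is kit receipt or clinic attendance at Month 6. In the intervention arm "an RA will collect the following data either in the field or at the study site (within the next two weeks"). The follow-up mediator is therefore recorded at or after the outcomes. Suppose, as assumptions, outcome rates of 40% and 60%, no true mediation, a baseline-to-Month-6 correlation of 0.5, a direct arm effect of 0.2 to 0.5 SD on the mediator, and a reverse effect of the outcome on the mediator of 0.1 to 0.5 SD. The share falsely attributed to mediation is then about 3% to 34% without baseline adjustment and 4% to 45% with it. With no reverse effect it is zero.

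**The case against.** The strongest reply is that both arms probably answer after allocation. The intervention-arm sentence stands under a heading that presupposes assignment, so the arms are symmetric in timing. This stands. A reader who sets the two sections side by side might infer that the arms are measured at different points, but the documents do not establish that. What remains is that answers are given knowing the arm, and symmetric timing does not remove this.

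Second, the arm odds ratio may never be reported. For the primary outcomes the models look for influencing factors, and the plan does not say that arm is included or that an adjusted arm effect is given. This also stands. The figures of 0.81 and 1.23 are conditional, and fit the secondary models of observed differences better. With arm in the model, the covariate's own odds ratio hardly moves.

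Third, the mediation analysis is already labelled exploratory and has sensitivity analyses. That is fair, and the timing of the mediators would not justify a finding by itself. The plan does not, however, say that those analyses cover the time order of mediator and outcome.

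**Conclusion.** The point holds as a minor one. The control-arm baseline questionnaire explicitly follows open allocation, and the intervention arm's probably does too, so the self-reported baseline scores are not protected pre-allocation values. The effect may be near zero. At the upper end assumed here (0.3 SD, odds ratio 2 per SD), a null arm odds ratio would move to about 0.81 or 1.23, roughly 0.4 standard errors at 40 per arm and 0.5 at 60. This applies only if arm is in the model and its adjusted effect is reported.

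Two stronger readings are not supported. One is that the trial's main comparison is biased: the Chi-square tests use no questionnaire data. The other is that the mediation analysis is invalid: it is exploratory, and its limitation is that it cannot establish direction. The 3% to 45% range shows only that the false share depends heavily on assumed inputs; it does not predict the trial's result.

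**What to change.** 1. In Consent, enrollment, and randomization, Intervention condition and Control condition, state one rule for both arms: the baseline questionnaire is completed after consent and before the numbered envelope is opened. Delete the opening two words of the Control condition sentence.
2. In Analysis, state that these pre-allocation values, not the Month 6 values, are the regression covariates and the baseline adjustment in the mediation analysis.
3. As a courtesy to readers, add that the follow-up mediator values do not precede the Month 6 outcomes and so cannot establish direction, and say whether the planned sensitivity analyses address time order. Baseline adjustment alone does not remove this error.

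The cost is a change of order within an enrolment visit already estimated at about 2 hours, plus a few sentences. Sample size, power and objectives do not change. The documents do not say whether enrolment has begun. If it has, item 1 applies only to participants not yet enrolled, and the report should say which baseline scores were taken after allocation.
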